7.0 MEASUREMENT OF EFFECT

7.1 Antitumor Effect- Solid Tumors

Response and progression will be evaluated in this study using the new international criteria proposed by the Response Evaluation Criteria in Solid Tumors (RECIST) Committee [JNCI 92(3):205-216, 2000]. Changes in only the largest diameter (unidimensional measurement) of the tumor lesions are used in the RECIST v1.1 criteria.

Definitions

Evaluable for toxicity. All patients will be evaluable for toxicity from the time of their first treatment with study drug.

Evaluable for objective response. Only those patients who have measurable disease present at baseline, have received at least 1 dose of pembrolizumab and have had their disease re-evaluated will be considered evaluable for response. These patients will have their response classified according to the definitions stated below. (Note: Patients who exhibit objective disease progression prior to the end of cycle 1 will also be considered evaluable.)

Disease Parameters

Measurable disease. Measurable lesions are defined as those that can be accurately measured in at least one dimension (longest diameter in the plane of measurement is to be recorded) with a minimum size of:

- 10mm by CT scan (irrespective of scanner type) for studies with a slice thickness of ≤ 5 mm or twice the slice thickness or MRI
- 10mm caliper measurement by clinical exam (lesions which cannot be accurately measured with calipers should be recorded as non-measurable)
- 20mm by chest X-ray (if clearly defined and surrounded by aerated lung)

All tumor measurements must be recorded in millimeters (or decimal fractions of centimeters)

Malignant lymph nodes: To be considered pathologically enlarged and measurable, a lymph node must be ≥ 15 mm in short axis when assessed by CT scan (CT scan slice thickness recommended to be no greater than 5 mm). At baseline and in follow-up, only the short axis will be measured and followed.

Non-measurable disease. All other lesions (or sites of disease), including small lesions (longest diameter <20 mm with conventional techniques or <10 mm using CT scan), are considered non-measurable disease. Bone lesions, leptomeningeal disease, ascites, pleural/pericardial effusions, lymphangitis cutis/pulmonis, inflammatory breast disease, abdominal masses (not followed by CT or MRI), and cystic lesions are all non-measurable.

Target lesions. All measurable lesions up to a maximum of 2 lesions per organ and 5 lesions in total should be identified as **target lesions** and recorded and measured at baseline. Target lesions should be selected on the basis of their size (lesions with the longest diameter), be representative of all involved organ, but in addition should be those that lend themselves to reproducible repeated measurements.

Lymph nodes merit special mention since they are normal anatomical structures which may be visible by imaging even if not involved by tumor. Pathological nodes which are defined as measurable and may be identified as target lesions must meet the criterion of a short axis of ≥ 15 mm by CT scan. Only the short axis of these nodes will contribute to the baseline sum. The short axis of the node is the diameter normally used by radiologists to judge if a node is involved by solid tumor. Nodal size is normally reported as two dimensions in the plane in which the image is obtained (for CT scan this is almost always the axial plane; for MRI the plane of acquisition may be axial, sagittal or coronal). The smaller of these measures is the short axis. For example, an abdominal node which is reported as being 20mm x 30mm has a short axis of 20mm and qualifies as a malignant, measurable node. In this example, 20mm should be recorded as the node measurement. All other pathological nodes (those with short axis ≥ 10 mm but <15 mm) should be considered non-target lesions. Nodes that have a short axis <10mm are considered non-pathological and should not be recorded or followed. A sum of the diameters (longest for non-nodal lesions, short axis for nodal lesions) for all target lesions will be calculated and reported as the baseline sum diameters. If lymph nodes are to be included in the sum, then as noted above, only the short axis is added into the sum. The baseline sum diameters will be used as reference to further characterize any objective tumor regression in the measurable dimension of the disease.

Non-target lesions. All other lesions (or sites of disease) including pathological lymph nodes should be identified as non-target lesions and should also be recorded at baseline. Measurements are not required and these lesions should be followed as 'present', 'absent', or in rare cases 'unequivocal progression' (more details to follow). In addition, it is possible to record multiple non-target lesions involving the same organ as a single item on the case record form (e.g. 'multiple enlarged pelvic lymph nodes' or 'multiple liver metastases').

Guidelines for Evaluation of Measurable Disease

All measurements should be recorded in metric notation, using calipers if clinically assessed. All baseline evaluations should be performed as close as possible to the treatment start and never more than 4 weeks before the beginning of the treatment.

The same method of assessment and the same technique should be used to characterize each identified and reported lesion at baseline and during follow-up. Imaging based evaluation should always be done rather than clinical examination unless the lesion(s) being followed cannot be imaged but are assessable by clinical exam.

Clinical lesions: Clinical lesions will only be considered measurable when they are superficial and >10mm diameter as assessed using calipers (e.g. skin

nodules). For the case of skin lesions, documentation by color photography including a ruler to estimate the size of the lesion is suggested. As noted above, when lesions can be evaluated by both clinical exam and imaging, imaging evaluation should be undertaken since it is more objective and may also be reviewed at the end of the study.

Chest X-ray: Chest CT is preferred over chest X-ray, particularly when progression is an important endpoint, since CT is more sensitive than X-ray, particularly in identifying new lesions. However, lesions on chest X-ray may be considered measurable if they are clearly defined and surrounded by aerated lung.

CT, MRI: CT is the best currently available and reproducible method to measure lesions selected for response assessment. This guideline has defined measurability of lesions on CT scan based on the assumption that CT slice thickness is 5mm or less. When CT scans have slice thickness greater than 5 mm, the minimum size for a measurable lesion should be twice the slice thickness. MRI is also acceptable in certain situations (e.g. for body scans).

Ultrasound: Ultrasound is not useful in assessment of lesion size and should not be used as a method of measurement. Ultrasound examinations cannot be reproduced in their entirety for independent review at a later date and, because they are operator dependent, it cannot be guaranteed that the same technique and measurements will be taken from one assessment to the next. If new lesions are identified by ultrasound in the course of the study, confirmation by CT or MRI is advised. If there is concern about radiation exposure at CT, MRI may be used instead of CT in selected instances.

Endoscopy, laparoscopy: The utilization of these techniques for objective tumor evaluation is not advised. However, they can be useful to confirm complete pathological response when biopsies are obtained or to determine relapse in trials where recurrence following complete response or surgical resection is an endpoint.

Tumor markers: Tumor markers alone cannot be used to assess objective tumor response. If markers are initially above the upper normal limit, however, they must normalize for a patient to be considered in complete response. Because tumor markers are disease specific, instructions for their measurement should be incorporated into protocols on a disease specific basis. Specific guidelines for both CA-125 response (in recurrent ovarian cancer) and PSA response (in recurrent prostate cancer), have been published. In addition, the Gynecologic Cancer Intergroup has developed CA125 progression criteria which are to be integrated with objective tumor assessment for use in first-line trials in ovarian cancer.

Cytology, Histology: These techniques can be used to differentiate between PR and CR in rare cases if required by protocol (for example, residual lesions in tumor types such as germ cell tumors, where known residual benign tumors can remain). When effusions are known to be a potential adverse effect of treatment (e.g. with certain taxane compounds or angiogenesis inhibitors), the cytological confirmation of the neoplastic origin of any effusion that appears or worsens during treatment can be considered if the measurable tumor has met criteria for response or stable disease in order to differentiate between response (or stable disease) and progressive disease.

Response Criteria

Evaluation of Target Lesions

Complete Response (CR): Disappearance of all target lesions, determined by two separate observations conducted not less than 4 weeks apart. There can be no appearance of new lesions.

Partial Response (PR): At least a 30% decrease in the sum of the longest diameter (LD) of target lesions, taking as reference the baseline sum LD. There can be no appearance of new lesions.

Progressive Disease (PD): At least a 20% increase in the sum of the LD of target lesions, plus a minimum 5 mm increase, taking as reference the smallest sum LD recorded since the treatment started, or the appearance of one or more new lesions.

Stable Disease (SD): Neither sufficient shrinkage to qualify for PR nor sufficient increase to qualify for PD, taking as reference the smallest sum LD since the treatment started.

Evaluation of Non-Target Lesions

Complete Response (CR): Disappearance of all non-target lesions and normalization of tumor marker level.

Incomplete Response/Stable Disease (SD): Persistence of one or more non-target lesion(s) and/or maintenance of tumor marker level above the normal limits.

Progressive Disease (PD): Appearance of one or more new lesions and/or unequivocal progression of existing non-target lesions.

Evaluation of Best Overall Response

The best overall response is the best response recorded from the start of the treatment until disease progression/recurrence (taking as reference for progressive disease the smallest measurements recorded since the treatment started). The patient's best response assignment will depend on the achievement of both measurement and confirmation criteria.

Target Lesions	Non-Target Lesions	New Lesions	Overall Response	Best Response for this Category Also Requires:
CR	CR	No	CR	≥4 wks. confirmation
CR	Non-CR/SD	No	PR	≥4 wks. confirmation
PR	Non-PD	No	PR	
SD	Non-PD	No	SD	Documented at least once ≥4 wks. from baseline
PD	Any	Yes or No	PD	no prior SD, PR or CR
Any	PD*	Yes or No	PD	
Any	Any	Yes	PD	
* In exceptional circumstances, unequivocal progression in non-target lesions may be accepted as disease progression.				

Note: Patients with a global deterioration of health status requiring discontinuation of treatment without objective evidence of disease progression at that time should be reported as “*symptomatic deterioration*”. Every effort should be made to document the objective progression even after discontinuation of treatment.

Note: If subjects respond to treatment and are able to have their disease resected, the patient’s response will be assessed prior to the surgery.

Duration of Response

Duration of overall response: The duration of overall response is measured from the time measurement criteria are met for CR or PR (whichever is first recorded) until the first date that recurrent or progressive disease is objectively documented (taking as reference for progressive disease the smallest measurements recorded since the treatment started).

The duration of overall CR is measured from the time measurement criteria are first met for CR until the first date that recurrent disease is objectively documented.

Duration of stable disease: Stable disease is measured from the start of the treatment until the criteria for progression are met, taking as reference the smallest measurements recorded since the treatment started.

Progression-Free Survival

Progression-free survival (PFS) is defined as the duration of time from start of treatment to time of progression or death, whichever occurs first. Patients without progression or death will be censored at the date of their last scan.

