2.2 Secondary Objectives

1. To determine the safety of the combination of SBRT and pembrolizumab in patients with platinum-refractory metastatic urothelial carcinoma.
2. To determine the anti-tumor efficacy of the combination of SBRT and pembrolizumab in patients with platinum-refractory metastatic urothelial carcinoma.

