3.1 Inclusion Criteria

- 3.1.1 Subjects must have a histologic diagnosis of urothelial carcinoma
- 3.1.2 Subjects must have radiologic evidence of metastatic disease with measurable disease by RECIST 1.1 criteria other than the target lesion(s) for SBRT
- 3.1.3 Subjects must have at least 1 metastatic lesion previously not radiated that is amenable to SBRT per treating radiation oncologist.
- 3.1.4 Subjects must have had progression of disease within 12 months of platinum-containing chemotherapy (chemotherapy could have been given in the neoadjuvant, adjuvant or metastatic setting) for urothelial cancer
- 3.1.5 ECOG performance status of 0 to 2
- 3.1.6 Absolute neutrophil count of $\geq 1000/\text{mm}^3$, platelet count $\geq 100,000/\text{mm}^3$, hemoglobin ≥ 8.0 g/dl; total bilirubin/ALT/AST < 2.5 x upper limit of normal (patients with known gilbert disease who have serum bilirubin ≤ 3 x ULN may be enrolled); serum creatinine < 3.0 mg/dl or if elevated, a calculated estimated glomerular filtration rate (eGFR) of ≥ 30 mL/min/1.73 m²
- 3.1.7 Subjects must have recovered to baseline or \leq grade 1 CTCAE v 4.03 from toxicities related to any prior treatments unless AE(s) are clinically non-significant and/or stable on supportive therapy
- 3.1.8 Subjects must be ≥ 2 weeks from most recent systemic therapy or most recent radiation therapy
- 3.1.9 Women of childbearing potential must have a negative serum or urine pregnancy test within 28 days prior to registration. Women of non-childbearing potential are defined as those who have no uterus, ligation of the fallopian tubes, are naturally postmenopausal for at least 12 consecutive months or have undergone surgical removal of the ovaries. Women of childbearing potential should use highly effective contraception during treatment and for 6 months after the last dose of pembrolizumab
- 3.1.10 Age ≥ 18 years

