5.0 TREATMENT PLAN

5.1 Treatment Dosage and Administration

Protocol treatment must start within 14 business days of enrollment to the study.

5.1.1 Therapy will include pembrolizumab 200 mg IV starting on day 1 in 21 day cycles. Patients will receive 1 dose (cycle 1) of pembrolizumab and commence SBRT no later than initiation of cycle 2.

5.1.2 SBRT will be given to ≥ 1 metastatic lesion(s) deemed most appropriate for such therapy by the treating radiation oncologist. SBRT will be delivered in 3 or 5 fractions with dose and fractionation selected to respect standard normal tissue dose constraints for adjacent organs at risk. See section 5.3 for further details.

5.1.3 The lesion to which SBRT is given will be identified after the patient receives 1 dose of pembrolizumab

5.1.3 Patients will be treated with supportive care pre-medications as clinically indicated including anti-emetics.

REGIMEN DESCRIPTION					
Agent	Premedications	Dose	Route	Schedule	Cycle Length
Pembrolizumab	None mandated	200 mg	IV	Once every 21 days (+/- 3 business days)	
SBRT	None mandated	3-5 fractions with dose and fractionation selected to respect standard normal tissue dose constraints for the relevant organs in the vicinity of the target lesion(s).	n/a	In cycle 1 any time after D1 and will commence no later than initiation of cycle 2	

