5.3 Stereotactic Body Radiotherapy

Stereotactic body radiotherapy (SBRT) involves advanced planning and delivery techniques to administer ablative doses of radiation to a target in a small number of fractions (treatment sessions). This has radiobiologic advantages and has been shown to be safe in numerous settings. A high priority is placed on minimizing exposure to surrounding normal tissues. Patients on this protocol will receive between three and five fractions of treatment. The dose per fraction will be determined per standard clinical practice and will be dependent on the location of the treated site and the adjacent organs at risk. SBRT will commence no later than initiation of the second cycle of pembrolizumab.

Both 3D-conformal radiotherapy and intensity-modulated radiotherapy (including volumetric arc radiotherapy [VMAT]) are acceptable planning techniques. Daily image guidance is required for this study.

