5.6 Duration of Therapy

In the absence of treatment delays due to adverse events, treatment will continue for 17 cycles or until one of the following criteria apply:

- Disease progression as defined in Section 7.0
- Patients may continue on pembrolizumab beyond the first progression by imaging as long as investigator deemed clinical benefit continues
- Inter-current illness that prevents further administration of treatment
- Unacceptable adverse event(s) or death
- Patient voluntarily withdraws from treatment
- General or specific changes in the patient's condition render the patient unacceptable for further treatment in the judgment of the investigator

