- **Immune-Related Best Overall Response Using irRC (irBOR)** irBOR is the best confirmed irRC overall response over the study as a whole, recorded between the date of first dose until the last tumor assessment before subsequent therapy (except for local palliative radiotherapy for painful bone lesions) for the individual subject in the study. For the assessment of irBOR, all available assessments per subject are considered. irCR or irPR determinations included in the irBOR assessment must be confirmed by a second (confirmatory) evaluation meeting the criteria for response and performed no less than 4 weeks after the criteria for response are first met.

Derivation of irRC overall responses

Measurable Response	Nonmeasurable Response		Overall Response
Index and new, measurable lesions (tumor burden),*%	Non-index lesions	New, non-Measurable lesions	Using irRC
↓100	Absent	Absent	irCR†
↓100	Stable	Any	irPR†
↓100	Unequivocal Progression	Any	irPR†
↓≥50	Any/Stable	Any	irPR†
↓≥50	Unequivocal Progression	Any	irPR†
↓<50 to <25↑	Any/Stable	Any	irSD
↓<50 to <25↑	Unequivocal Progression	Any	irSD
25	Any	Any	irPD†

*Decreases assessed relative to baseline (scan prior to start of any protocol therapy), including measurable lesions only

†Assuming response (irCR) and progression (irPD) are confirmed by a second, consecutive assessment at least 4 wk apart.

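### A lesion treated with protocol SBRT can stay in the RECIST and irRC sums, and no ORR or PFS is planned on the non-irradiated measurable disease

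*Combined protocol and SAP*

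**What the plan says.** **Lesion selection.** Section 7.1 states that "All measurable lesions up to a maximum of 2 lesions per organ and 5 lesions in total should be identified as" target lesions, chosen on size, organ representation and repeatability of measurement. Section 7.2 builds the irRC burden from the products of diameters of all index lesions (5 per organ, up to 10 visceral). Both are fixed at baseline, and neither mentions SBRT.

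**Timing.** The first of the two items numbered 5.1.3 says "The lesion to which SBRT is given will be identified after the patient receives 1 dose of pembrolizumab". SBRT starts no later than cycle 2. The Time and Events Table (6.2) puts the first post-baseline scan at week 12. Section 5.3 describes SBRT as a technique "to administer ablative doses of radiation to a target in a small number of fractions".

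**Other disease.** Inclusion 3.1.2 requires "measurable disease by RECIST 1.1 criteria other than the target lesion(s) for SBRT". Sections 7 and 11 never assess that disease on its own.

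**Local treatment in Section 7.** Response is taken before any resection (7.1). The irBOR window in 7.2 runs to the last assessment before subsequent therapy, "except for local palliative radiotherapy for painful bone lesions". Nothing addresses protocol SBRT.

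**Thresholds.** RECIST PR is a 30% fall in the target sum. RECIST PD is a 20% rise, "plus a minimum 5 mm increase, taking as reference the smallest sum LD recorded since the treatment started", or new lesions. irPR is a 50% fall in burden and irPD a 25% rise.

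**Analysis.** The secondary objective is "To determine the anti-tumor efficacy of the combination of SBRT and pembrolizumab in patients with platinum-refractory metastatic urothelial carcinoma". Section 11.2 describes ORR and PFS by both criteria, in the evaluable and the treatment-success populations, with no split by irradiated lesion.

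**The concern.** The rationale in 1.3 rests partly on radiation shrinking distant tumours. Baseline lesions are fixed first and the SBRT lesion is identified afterwards, so a target lesion can be given ablative treatment and still count in the sum. Two things follow. A PR can reflect the irradiated lesion alone. Growth of the other targets can also be offset by local shrinkage, so that progression is recorded late.

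A reader of the planned ORR and PFS could not tell these apart from a response elsewhere. The treatment-success population is the most exposed, because by definition every patient in it received SBRT.

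The issue arises only when the SBRT lesion is measurable and selected; under 7.1 a bone lesion, for example, is not measurable.

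**Working it through.** The plan states no figure for ORR or PFS to reproduce. The only computed figure in Section 11 is the feasibility interval: 0.70 ± 1.96 × √(0.70 × 0.30/20) = 0.499 to 0.901, which matches the stated 50% to 90%. This point does not touch it.

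**Inputs.** The thresholds come from 7.1 and 7.2. Assumed, because the documents give no figures: k equal target lesions, one irradiated, with diameter shrinkage s of 30%, 50% or 70%. New and non-target lesions are left out of the model.

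**1. PR from local shrinkage alone, other targets unchanged.** The sum changes by −s/k, so PR needs s ≥ 0.30k: 0.60 for k=2 and 0.90 for k=3. For k=4 and k=5 it needs 1.20 and 1.50, which is impossible. For unequal lesions, if w is the SBRT lesion's share of the baseline sum, PR needs w ≥ 0.30/s: 60%, 40% or 30% of the sum for s of 50%, 75% or 100%.

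**2. Growth g of the other targets before PD at week 12.** The reference is the baseline sum. Setting (1−1/k)g − s/k = 0.20 gives g = (0.20 + s/k)/(1 − 1/k).

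**3. The same at a later scan.** The reference is the smallest sum. With the other targets flat to week 12 and the SBRT lesion stable afterwards, g = 0.20(k − s)/(k − 1).

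| Equal targets | Local shrinkage for PR | g at week 12, s = 30/50/70% | g later, s = 30/50/70% |
|---|---|---|---|
| 2 | 60% | 70 / 90 / 110% | 34 / 30 / 26% |
| 3 | 90% | 45 / 55 / 65% | 27 / 25 / 23% |
| 5 | not reachable | 32.5 / 37.5 / 42.5% | 23.5 / 22.5 / 21.5% |

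The last two columns assume reference sums of at least 25 mm, so that the 5 mm minimum does not bind.

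**4. The other targets judged alone.** PD needs growth of max(20%, 5 mm/sum): 20% at 25 mm or more, 25% at 20 mm, 50% at 10 mm.
- Two 20 mm targets, s = 50%: PD at 40 × 1.20 = 48 mm. The irradiated lesion is 10 mm, so the other must reach 38 mm (+90%, against +25% alone).
- Two 10 mm targets, s = 50%: PD at 20 + 5 = 25 mm. The irradiated lesion is 5 mm, so the other must reach 20 mm (+100%, against +50% alone).

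**5. irRC, two equal index lesions, s = 50% in both diameters.** The product falls by 1 − 0.5² = 75%. At the first scan the other lesion reaches the +25% threshold at (0.25 + 0.375)/0.5 = 125% growth by product, which is √2.25 − 1 = 50% in diameter. Alone it needs 25% by product, which is √1.25 − 1 = 11.8% in diameter. After nadir the figure is 0.25 × (2 − 0.75) = 31% by product. irPR from local shrinkage alone needs complete disappearance with two index lesions and is impossible with three or more equal ones.

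**6. Direction of any ORR effect.** The sum falls by 30% when the other targets change by (−0.30 + s/k)/(1 − 1/k). At s = 30% this is exactly −30%, so including the SBRT lesion changes nothing. Above 30% it makes a PR easier, and below 30% harder.

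**The case against.** The best defence is that 7.1 does set a default: lesions stay in the sum, and response over all lesions is what an objective about the combination calls for. No objective or endpoint in Section 2 names an out-of-field effect, which appears only in the rationale. That stands, and it is why the all-lesion result should remain the main one. It does not answer the concern that 3.1.2 secures separate measurable disease which the analysis then never uses.

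Four stronger readings may tempt a reader, and the documents do not support them.
- *The ORR is inflated.* The documents give no local shrinkage figure, and step 6 shows that the direction depends on it. Section 11 plans no comparison with the 21% ORR quoted for pembrolizumab.
- *Progression is hidden altogether.* Under RECIST, new lesions and unequivocal non-target progression still give PD. Under irRC the single-scan threshold shifts, but irPD must be confirmed at least 4 weeks later, so one scan does not establish it on either lesion set.
- *All other radiation is also unaddressed.* The irBOR wording arguably closes the window at later non-bone palliative radiation, and bone lesions are outside the measured sum. RECIST response and PFS have no such rule.
- *3.1.2 contradicts 5.1.3 on when the SBRT lesion is known.* Section 1.3 speaks of a lesion proposed for SBRT at entry, which is compatible with identifying it after dose 1.

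**Conclusion.** The point holds for the secondary efficacy endpoints. When the SBRT lesion is a target, mainly with two or three targets or a dominant SBRT lesion, a PR can reflect local ablation alone, and growth of other targets can be masked. The masking is largest at week 12: with two equal targets and 50% local shrinkage, growth of 90% is tolerated, falling to 30% at later scans. A progression hidden at week 12 is dated to the next scan at the earliest.

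These sizes rest on assumed lesion numbers, equal lesion sizes and assumed shrinkage. How often the situation will occur, and the net effect on ORR, cannot be computed from the documents. The affected analyses are descriptive. The primary endpoint, the 14/20 rule and N=20 do not change. It should be fixed before the data are analysed, but it does not threaten the trial's main conclusion.

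**What to change.** 1. In 7.1 and 7.2, record which target, non-target or index lesions receive protocol SBRT. With one SBRT lesion, 3.1.2 and the target caps already leave a measured non-irradiated lesion. Where more than one lesion may be irradiated, make sure that at least one non-irradiated measurable lesion is measured at baseline, since 7.1 does not require measurement of non-targets.
2. In 11.2, keep the all-lesion ORR and PFS as the main result for the combination. Add one sensitivity analysis in the evaluable population (RECIST, optionally irRC) with protocol-SBRT lesions removed from the sums at baseline and at all later scans. Report those lesions separately as local control.
3. Do not remove retrospectively any lesion given later palliative radiation under 5.4. Keep its assessments up to that radiation; otherwise the growth that prompted the treatment could be erased and PFS lengthened.
4. State that the added version is for analysis only. Section 5.6 lists "Disease progression as defined in Section 7.0" among the reasons to end treatment, and that definition should not change.

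**Cost.** Wording in three sections, a second sum per patient and occasional extra baseline measurements. Section 11.2 now yields 2 criteria × 2 populations = 4 ORRs and 4 PFS curves. The addition makes 5 of each with RECIST only, or 6 of each with irRC. There is no effect on sample size.

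### Section 7.1 measures lymph nodes by short axis but defines PR, SD and PD on longest diameters, and has no complete-response rule for a normalised node that is still visible

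*Combined protocol and SAP*

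**What the plan says.** All the relevant text is in Section 7.1 of the combined protocol and SAP.

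- **Opening paragraph:** "Changes in only the largest diameter (unidimensional measurement) of the tumor lesions are used in the RECIST v1.1 criteria".
- **Malignant lymph nodes:** a node is measurable from 15 mm short axis, and "At baseline and in follow-up, only the short axis will be measured and followed".
- **Target lesions:** "Only the short axis of these nodes will contribute to the baseline sum". The total is then defined: "A sum of the diameters (longest for non-nodal lesions, short axis for nodal lesions) for all target lesions will be calculated". Its purpose is also stated: "The baseline sum diameters will be used as reference to further characterize any objective tumor regression in the measurable dimension of the disease". A worked example records a 20 x 30 mm node as 20 mm.
- **Normal nodes:** the same paragraph accepts that uninvolved nodes can be seen on imaging, and adds "Nodes that have a short axis <10mm are considered non-pathological and should not be recorded or followed".
- **PR:** "At least a 30% decrease in the sum of the longest diameter (LD) of target lesions, taking as reference the baseline sum LD". SD and PD also use the longest-diameter sum. PD needs a rise of at least 20% and at least 5 mm over the smallest such sum since treatment began.
- **CR, target lesions:** "Disappearance of all target lesions, determined by two separate observations conducted not less than 4 weeks apart". Non-target CR also requires disappearance. Neither rule mentions nodes.

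**The concern.** The response categories refer to a baseline longest-diameter sum. For a patient with a nodal target, the target-lesion paragraph never produces that quantity. The opening paragraph supports the longest-diameter rule, and the two node paragraphs support the short-axis rule. An assessor can follow either one and point to text in the same section.

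Best overall response and PFS by RECIST are the efficacy secondary endpoints (Sections 2.4 and 11.1). Section 7.2 adds concordance between RECIST and irRC as a further secondary endpoint. All three depend on these categories. Nodal long axes will be available to an assessor who wants them, because irRC in Section 7.2 needs two perpendicular diameters of every index lesion.

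The CR rule has a separate gap. The section treats a node under 10 mm short axis as no longer pathological, but that threshold does not reach the CR definition.

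**Working it through.** **Inputs, all from Section 7.1.** Worked node 20 x 30 mm; target nodes at least 15 mm short axis; non-pathological below 10 mm; PR at least -30%; PD at least +20% and at least +5 mm; smallest measurable non-nodal lesion on CT 10 mm. The follow-up sizes below are illustrations.

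**Plan's own figure.** min(20, 30) = 20 mm, as the worked example says.

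**Step 1. Two consistent readers, node as the only target lesion.**

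| Node change (mm) | Short axis at both times | Longest diameter at both times |
|---|---|---|
| 20 x 30, unchanged | 0%, SD | 0%, SD |
| 20 x 30 to 13 x 25 | (13 - 20)/20 = -35%, PR | (25 - 30)/30 = -16.7%, SD |
| 20 x 30 to 9 x 22 | (9 - 20)/20 = -55%, PR | (22 - 30)/30 = -26.7%, SD |

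In the last row the node is non-pathological by the section's own threshold. Under the longest-diameter rule it is nevertheless neither CR nor PR while it stays visible.

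**Step 2. Dilution by other target lesions.** Let n be an unchanged non-nodal target sum in mm.
- For 13 x 25, PR on the short axis needs 7/(20 + n) >= 0.30, so n <= 3.3 mm. That is below the 10 mm minimum, so this contrast needs node-only target disease or other lesions that also shrink.
- For 9 x 22, PR needs 11/(20 + n) >= 0.30, so n <= 16.7 mm. At n = 10 the short axis gives 30 to 19 mm, -36.7% (PR). The longest diameter gives 40 to 32 mm, -20% (SD).

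**Step 3. Progression, again with consistent readers.** Take a sole 20 x 30 mm node whose baseline is also its nadir.
- Short axis: 20% of 20 is 4 mm, so the 5 mm minimum governs and PD starts at 25 mm.
- Longest diameter: 20% of 30 is 6 mm, so PD starts at 36 mm.
- A node that reaches 25 mm short axis while its long axis is below 36 mm is PD for one reader and not for the other. This is how PFS is affected.

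**Step 4. The CR gap.** Suppose the non-nodal targets have gone and every target node has fallen from at least 15 mm to below 10 mm short axis. Each node has shrunk by more than (15 - 10)/15 = 33.3%, so the sum has fallen by more than 30% and the patient is at least PR. A visible normalised non-target node has the same effect: the response table scores target CR with non-target non-CR as PR. With the short axis throughout, the gap therefore moves patients between CR and PR, and changes duration of CR. It does not change the pooled CR + PR proportion analysed in Section 11.2.

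**Step 5. Weight of one patient.** 1/20 = 5 percentage points, taking all 20 planned patients as evaluable for response.

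**The case against.** The strongest reply is that the section settles the matter itself. The lymph-node paragraph requires the short axis at follow-up as well as at baseline, and the evaluation guidelines require the same method and technique at both times. On that view the longest-diameter wording is leftover text that a trained assessor would read past. It is indeed the better reading of the section as a whole. But the opening sentence and three response categories say otherwise, and nothing states which text governs.

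Two stronger readings are tempting, and the documents do not support them.

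- **Unchanged nodal disease is scored as progression.** This needs the short axis at baseline and the longest diameter at follow-up, contrary to the lymph-node paragraph. A consistent rule of either kind gives 0%. Even with mixed axes, the 20 x 30 mm node yields PD only if 10/(20 + n) >= 0.20, that is, n <= 30 mm. At n = 30 the change is 50 to 60 mm, +20.0%; at 31 it is 51 to 61 mm, +19.6%. This is a misapplication risk, not a result of the plan.
- **A normalised node can never be CR.** A node that is no longer visible has disappeared. The instruction not to record or follow nodes under 10 mm also gives an assessor grounds to treat the node as gone. CR is withheld only on a literal reading, while the node remains visible.

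It is also fair to say that a scored progression does not automatically end treatment, because Section 5.6 allows continuation after a first radiological progression if the investigator sees benefit. The primary endpoint is essentially untouched. Its only link is the exclusion of patients with a complete response before SBRT, and the study calendar schedules no imaging between screening and week 12.

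**Conclusion.** The contradiction is real and should be corrected. Following the PR, SD and PD definitions as written gives different classifications from following the nodal measurement rule, even when each reader is internally consistent. The clearest example is -35% (PR) against -16.7% (SD) for node-only target disease.

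The consequences are limited to best overall response, PFS and RECIST-irRC concordance, all secondary, and to duration of CR. Each patient reclassified as responder or non-responder moves a response proportion out of 20 by 5 points. How many would be affected cannot be estimated, because the documents do not give the share of patients with nodal targets. The conclusion that the CR gap leaves pooled CR + PR unchanged holds only if nodes are measured on the short axis throughout. Under the longest-diameter rule it can fail, as the 9 x 22 mm node shows.

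**What to change.** Amend Section 7.1 in its own terms:

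1. In PR, PD and SD, replace the longest-diameter sum, and the baseline or smallest version of it, with the sum of diameters defined in the target-lesion paragraph.
2. Reword the opening sentence so that it excepts nodes, which are measured by short axis.
3. State that, for CR, a target node counts as resolved once its short axis is below 10 mm, the threshold the section already uses.
4. State that a non-target node is recorded as absent below 10 mm short axis. Align the non-target paragraph, which at present requires no measurements of these lesions.

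The cost is a text amendment plus a short-axis check of non-target nodes, on existing scans, when CR is being considered. No new scans are needed.
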